#### 6.4 Consent

The process for obtaining participant informed consent will be in accordance with ethical guidelines and Good Clinical Practice. Potential participants from the INSPIRE study will be asked whether they wish to consider taking part, emphasising that participation is entirely voluntary. The participant information sheet, questionnaire and consent form will be sent by email to interested INSPIRE study Ppts, and made available online if INSPIRE Ppts do not generate sufficient numbers. There will be an opportunity to ask questions. Consent for both phases of the psychosocial trials (including to potentially be interviewed) will be requested electronically at the start of the baseline questionnaires. Consent for the interview and to be audio-recorded will also be verbally taken at the start of the interview with the consent statements audio recorded.

#### 6.5 Participant withdrawal

Participants may be withdrawn from the intervention groups and/or the whole study either at their own request, at the request of the intervention provider or at the discretion of the investigator. Participants will be made aware from the information sheet and in the allocation of group letter of how to withdraw and that it will not affect their medical care. Participants will be given the contact details of research staff and informed of how to report unacceptable or unkind behaviour within their intervention group. Participants whose behaviour is not acceptable or unkind will be initially warned for more minor issues and/or withdrawn from the group by study staff.

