# 4 Study Synopsis

Study title	The ADAPT study (Adapting, Disease self-management and							
	Acknowledgement through Psychosocial Targeted interventions)							
Short title	The ADAPT study							
Principal	[name] and [name]							
Investigators								
Chief Investigators'	University of Cambridge							
employing Institution								
Study sponsor	University of Cambridge							
Funder	LUPUS UK and The Lupus Trust							
	·							
Study Duration	3 years (over 2 phases)							
Participants								
Sample size	Phase 1							
	N=120 (n=30 in each of the 3 intervention groups of text messaging							
	intervention, listening support (The Wren Project) and the online physical							
	activity course (Flexifit Pilates) and n=30 in control.							
	Phase 2							
	N=800 (approximately)							
	Numbers dependent on which interventions progress to phase 2, and sample size calculations informed by phase 1. Provisional estimates of N=100 for online physical activity, N=100 for The Wren support, N= 300 for							
	text messaging support and N=300 control.							
	Process and acceptability evaluation interviews with phase 1 participants will take place until theoretical saturation (the point at which no new concepts are generated) is reached. Estimated 15 for each intervention group.							
Objectives	Aim							
	To assess the acceptability, feasibility and effectiveness of methods of remote psychosocial support for SARDs patients. For the interventions trialled (if effective and acceptable) to be incorporated as an adjunct to usual care.							
	Objectives							
	To trial multiple quality of life and mental health measures to determine the most appropriate primary and secondary outcomes for phase 2.							
	To test processes to inform phase 2 effectiveness trial.							
	To develop and trial our own ADAPT instrument to more accurately							

	reflect, measure and monitor SARD patient personal, social and medical satisfaction.  • To assess the acceptability (phase 1) and effectiveness (phase 2) of remote psychosocial interventions on the mental health, wellbeing, self-esteem, resilience, loneliness and disease acceptance of patients with systemic autoimmune rheumatic diseases.

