## Progression of interventions to phase two.

In phase one, we will be evaluating various potential outcome measures for phase two whilst also ascertaining acceptability and feasibility of the three interventions to progress to phase 2. Phase two will be assessing the effectiveness of any interventions that progress to phase 2. Further selection criteria are explained below.

Interventions will only progress to phase two (effectiveness trial) if there is a high degree of acceptability and feasibility demonstrated in phase 1. Thresholds for progression to phase two are:

- 1. Green: Progress to phase 2 if >75% of phase 1 participants are satisfied/ very satisfied with the support and engaged with the support.
- 2. Amber: Consider progression to phase 2 with study team, charity, and patient group discussion, and if intervention acceptability and engagement can be feasibly improved, if between 50-75% of participants are satisfied and engaged with the support.
- 3. Red: Do not progress any intervention where <50% of participants are satisfied and engaged.

In addition, interventions that are found to not be feasible for the providers or the research team to progress to larger numbers in phase 2 will be excluded. Interventions may be trialled together for comparison or may be separate trials with separate control groups for phase two depending on phase one findings.

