We will also assess the association between pre-defined pairs of variables of interest ) using Pearson correlation coefficient with Chi- Square test. T-tests, Wilcoxon-Mann Whitney tests, Chi-Square tests, Kruskal Wallis tests and one-way/factorial ANOVA will be used appropriately to compare the mean scores, frequencies and impact between groups of patients. Regression models will be used to assess the effect of multiple variables on specific outcomes. As this is a very unexplored area, some additional exploratory analysis will occur in addition to pre-specified measures in order to identify priorities for future research.

Prior to the main analysis, we will conduct data cleaning. Percentages of invalid values, outliers and missing data will be reported. We will also investigate any patterns of missing data. Where appropriate, theoretical and/or clinical criteria will be used to identify invalid values or outliers. Depending on their type and prevalence we will decide on the most appropriate way of addressing. Our options include data exclusion from the rest of the analysis, data replacement with mean or mode values, or data inclusion as separate category (in case of missing data). Our primary option is to conduct "complete-case" analyses. We will not use multiple imputation for missing data. In case of highly prevalent missing data (more than 10% of the sample), sensitivities analyses based on the other option of missing data addressing will be used to assess the robustness of our findings.

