## 7.5 Adverse Incident reporting

As this study is not a 'clinical trial of an investigational medicinal product (CTIMP)' it does not fall under The Medicines for Human Use (Clinical Trials) Regulations 2004 (as amended).

The research team will not collect data on adverse events (AEs), serious adverse events (SAEs) or suspected unexpected serious adverse reactions (SUSARs) as defined by these regulations. However, even in non-pharmaceutical research, such as this study, adverse incidents may still happen, for example:

- breach of confidentiality
- patient complains about any aspect of study
- deviation from study protocol (e.g. recruiting before consent)
- equipment failure
- aggressive/ unacceptable behaviour of a participant towards the support group, researcher, staff or others.
- Responses highlight serious concern of risk to a patient

Concerns of risk to a participant will be immediately reported to the relevant authorities and the Chief Investigator. Unacceptable behaviour within support groups will result in expulsion of that participant from the group. Adverse incidents relating to the conduct of this research must be reported to the Chief Investigator within 5 working days of any team member becoming aware of the incident.

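### Section 6.5 lets an intervention provider request a randomised participant's withdrawal from the whole study, with no criteria or continued follow-up stated; this can bias the complete-case comparison.

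*Protocol*

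**What the plan says.** Section 6.5 of the protocol sets out who may end a participant's involvement and from what: "Participants may be withdrawn from the intervention groups and/or the whole study either at their own request, at the request of the intervention provider". The sentence goes on to add the investigator: "at the request of the intervention provider or at the discretion of the investigator". Withdrawal from the group and withdrawal from the study are thus two separate options, and each is open to the participant, the provider and the investigator.

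The only ground that the protocol states is behaviour, and there the consequence is loss of the group. Section 6.5 says: "Participants whose behaviour is not acceptable or unkind will be initially warned for more minor issues and/or withdrawn from the group by study staff". Section 7.5 agrees: "Unacceptable behaviour within support groups will result in expulsion of that participant from the group". No ground is given for a provider to request withdrawal from the whole study. Nothing says whether someone removed at a provider's request still receives the 12-week and 6-month questionnaires.

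On analysis, section 6.7 (Analysis and outcome measures) states: "Our primary option is to conduct 'complete-case' analyses". It excludes multiple imputation and provides sensitivity analyses when more than 10% of the sample is missing.

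On progression, section 6.1 sets Green as "Progress to phase 2 if >75% of phase 1 participants are satisfied/ very satisfied with the support and engaged with the support" and Red as "Red: Do not progress any intervention where <50% of participants are satisfied and engaged". It does not say whether withdrawn participants remain in the denominator.

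**The concern.** Leaving an intervention need not cost the trial any data; leaving the study does. Section 6.5 lets the provider, who is not the participant, ask for the second. Controls have no provider, so a loss of this kind can arise only in an intervention arm, and it happens after randomisation.

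If the people removed would have had worse outcomes than the rest of their arm, a complete-case analysis compares a selected intervention group with an unselected control group, and the selection favours the intervention. If they would have had better outcomes, the bias runs the other way. No analysis plan can recover questionnaires that were never sent.

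Phase 1 has a second exposure. Each intervention is judged on the percentage satisfied and engaged among about 30 people, so one person can move the result across a threshold. If removed participants drop out of the denominator, a provider's request could affect the result by which its own intervention is judged.

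**Working it through.** **Inputs from the protocol.** The synopsis gives "N=120 (n=30 in each of the 3 intervention groups of text messaging" and 30 controls: 4 x 30 = 120, as stated. The provisional phase 2 sizes are 100 + 100 + 300 + 300 = 800, also as stated. Green is above 75% and Red is below 50%. The trigger for missing-data sensitivity analyses is more than 10% of the sample. The protocol gives no removal rate and no effect size for this, so everything below that depends on them is an assumption.

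**Shift in the complete-case mean.** Let a fraction p of an arm be removed, with outcomes d SD below the mean of the whole arm. The mean of those remaining rises by p/(1-p) x d.
- p = 0.10, d = 1: 0.10/0.90 = 0.111 SD.
- p = 0.05, d = 1: 0.05/0.95 = 0.053 SD.
- If d = 1 is measured against those remaining instead, the shift is p x d: 0.10 and 0.05 SD.
- If removal is unrelated to outcome, d = 0 and there is no systematic shift.

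**Effect on a two-sided 5% test, 100 v 300, no true effect.** The standard error is sqrt(1/100 + 1/300) = 0.1155 SD. The rejection probability is Phi(-1.96 + shift/SE) + Phi(-1.96 - shift/SE).

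| Removed | Shift (SD) | Shift/SE | Rejection |
|---|---|---|---|
| 10% | 0.111 | 0.96 | 16.1% |
| 5% | 0.053 | 0.46 | 7.4% |

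With the reduced arm of 90, the SE is 0.120 and the first row becomes 15.2%. With a shift of 0.10 SD and 90 v 300 it is 13.2%. With an arm of 95 the second row stays at about 7%.

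**Phase 1 scale.** For 30 v 30 the SE of a difference is sqrt(2/30) = 0.258 SD. Three removals at d = 1 shift the arm mean by 3/27 = 0.111 SD, well inside the noise of a pilot comparison.

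**The sensitivity-analysis trigger.** Three removals from one arm are 3/30 = 10% of that arm but 3/120 = 2.5% of the phase 1 sample. They would not exceed the 10% trigger on their own.

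**Progression, if withdrawn participants leave the denominator.** With all 30 retained, Green needs at least 23/30 (76.7%).

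| Satisfied and engaged | All 30 kept | Removed, none of them satisfied and engaged | Change |
|---|---|---|---|
| 22 | 73.3% | 1 removed: 22/29 = 75.9% | Amber to Green |
| 21 | 70.0% | 3 removed: 21/27 = 77.8% | Amber to Green |
| 14 | 46.7% | 2 removed: 14/28 = 50.0% | Red to Amber |

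At a true rate of 70%, the binomial probability of Green is 0.281 with no removals. It is 0.432 with one and 0.589 with three, if all those removed are from the unsatisfied. If removal is unrelated to satisfaction, it is 0.281, 0.321, 0.220 and 0.256 for none to three removals. That has no upward trend and reflects only the rounding of the cut-off.

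**The case against.** The case against is substantial, and most of it stands as a limit on the point.

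- **Group and study withdrawal are not merged.** A reader might infer that section 6.5 treats them as one step. Its wording offers them as alternatives, and the only stated ground, behaviour, costs the participant the group and not the study.
- **The investigator's discretion is not one-sided.** It applies to any participant, controls included. Only the provider route lacks a control counterpart. Even that is clear only for listening support and Pilates, which have outside providers. The text arm consists of automated messages and WhatsApp groups that a researcher sets up and then leaves.
- **Bias towards the interventions is not established.** It needs the removed people to be those doing badly. The protocol does not say so, and poor behaviour is not the same as a poor outcome. The rates above are assumptions, and ten provider-requested removals in 100, each 1 SD worse, is a severe case.
- **The progression effect is conditional.** Section 6.1 does not drop withdrawn participants; it leaves the matter open. The 22/30 example begins at the one count where a single removal reaches Green. A provider can only make a request, and the study team takes the progression decision after meeting the advisory board.
- **Analysis sets and denominators often belong in a statistical analysis plan**, which is not shown here. Section 6.7 also promises to look at patterns of missing data.

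These points do not answer the core. A later plan can define who is analysed, but it cannot restore follow-up data lost because the protocol allowed withdrawal from the whole study. The fix must also leave the investigator able to stop contact, since section 7.5 foresees responses that raise serious concern about risk to a participant.

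**Conclusion.** The point holds in a limited form. Section 6.5 permits provider-requested withdrawal from the whole study, without criteria and without a statement that follow-up continues, and this can occur only in arms with a provider. Combined with primary complete-case analysis, no multiple imputation and a 10% trigger for sensitivity analyses, it can cause arm-dependent data loss and bias the comparison if those removed differ in outcome.

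The actual size is unknown and may be small. The illustrative error of about 7-16% rests on 5-10% removal, outcomes 1 SD below the arm mean, and the provisional sizes of 100 and 300. The change from Amber to Green after one removal rests on that person not being satisfied and engaged and on their leaving a denominator that the protocol does not define. The documents do not support the stronger inference that the plan does bias results towards the interventions. The change is worth making because it is cheap and protects the randomised comparison.

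**What to change.** In section 6.5 and the information sheet, state that a provider's request ends participation in the intervention group only. The participant is still sent the follow-up 1 and follow-up 2 questionnaires unless they themselves withdraw from data collection, or the investigator documents a reason for stopping contact, such as a concern about risk. They are analysed in the group to which they were randomised.

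In section 6.1, define the progression denominator as all participants randomised to the arm, and count those removed as not engaged.

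Who is removed from a group, and when, stays as written. The cost is a few sentences, a few more questionnaire emails, and possibly slightly lower progression percentages.

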#### 6.6 Data collection and participant follow-ups

Data collection will be both quantitative through surveys, and qualitative through open-ended survey responses and in-depth interviews with purposively selected Ppts following each intervention. In addition to the instruments listed below, questions will elicit sociodemographic data and acceptability of the instruments and the interventions. Interviews will explore intervention experiences and acceptability views in depth.

For phase 1 we will be trialling multiple potential outcome measures for phase 2. This includes:

- The UCLA 6 item loneliness scale (RULS-6)
- The Connor Davidson resilience scale
- GAD-7
- PHQ-8
- Our own ADAPT instrument (Appendix 1)
- FACIT-F
- EQ-5D-5L (https://eurogol.org/eq-5d-instruments/eq-5d-5l-about/)

In addition, for phase 2 we will be evaluating health and social care use, and costs borne by patients, measured using a retrospective resource use questionnaire, an adapted version of the Client Receipt Service Inventory (https://www.pssru.ac.uk/csri/what-is-the-csri/). Phase 1 assessment of costs will be qualitative to determine the appropriate categories for phase 2 costings.

#### **Economic analysis**

An economic analysis is warranted given the potential economic implications of the interventions, both in terms of the costs they will incur to deliver, and their impact on subsequent health service use. We will estimate costs and outcomes during 'within-trial' period only. Costs will be assessed from the perspective of the NHS and personal social services (PSS), and also from a wider societal perspective, which includes productivity loss and out of pocket costs incurred by participants and their families. We will undertake a cost consequences analysis, which is used to assess a wide range of costs and consequences (effects) and reports them separately (https://www.gov.uk/guidance/cost-consequence-analysis-health-economic-studies).

The economic analysis outcome measures will be EQ-5D-5L scores, quality-adjusted life years (QALYs) and the measures listed above (QALYs will be calculated based on the reported EQ-5D-5L scores using an 'area under the curve' approach). We will undertake a detailed micro-costing of each of the interventions during Phases 1 and 2. To measure other NHS, PSS and broader societal costs in Phase 1 we will undertake qualitative research to identify what cost components to include; these will then be measured retrospectively at each follow-up point in Phase 2. These are likely to include the following NHS contacts:

- GP contacts at the surgery, home or by telephone or videoconferencing
- Practice nurse contacts at the surgery, home or by telephone or videoconferencing
- Emergency Department visits
- Outpatient visits with the Rheumatologist
- Admitted patient stays
- Medications

We will also ask participants about their use of PSS and, in terms of broader societal costs, travel costs for families going to and from NHS visits, days taken off work, and any other out-of-pocket costs incurred (e.g., for medications or home adaptations).

Unit costs will be obtained from published sources and inflated where appropriate, before being applied to the volume of resource use data to calculate costs.

We will also be obtaining the level and impact of fatigue, pain, cognitive dysfunction on their lives and obtaining a self-assessment of level of disease activity.

An additional measure for the physical activity component will be a short physical ability test as measured by the flexifit instructor to include: strength, mobility and stamina.

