#### Data collection

Baseline survey: On entry into the ADAPT trial prior to being randomised to an intervention or the control group.

Follow-up 1: Baseline + 12 weeks.

Follow-up 2: Baseline + 6 months to more accurately ascertain potential longer-term effects.

In-depth interviews will be carried out with purposively selected participants from questionnaire responses. Interviews will also be carried out during the interventions (in phase 1 only) to assess views of different intervention components, in order to refine the interventions and processes for phase 2.

Analysis	Qualitative - Thematic analysis including using Nvivo 12 software								
	Quantitative – Descriptive and inferential statistics, including multiple regression analysis.								

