#### Follow-ups

Follow-up 1 - Baseline+ 12 weeks

Follow-up 2 - Baseline + 6 months

Participants will be sent up to 3 email reminders for non-response to the follow-up questionnaires.

#### 6.7 Selection of outcome measures for phase 2

Phase 2 primary and secondary outcome measures will be selected from the analysis of phase 1 quantitative and qualitative results. Following phase 1 analysis, the multidisciplinary ADAPT study team will meet to decide which intervention(s) will proceed to phase 2 and which outcome measures to select for phase 2. The selection criteria will include (with most weight given to patient views on importance):

- 1. Acceptability and perceived importance and relevance of each measure to patients. These will be assessed quantitively by questions on the survey about each instrument, and qualitatively during interviews. Any measures that are rated as unacceptable or irrelevant by >25% of participants will be excluded. Participants will be asked to rank the measures in terms of importance to them and a mean score calculated. The top 3 scoring outcome measures will be discussed, taking into account additional patient views from interviews, team views and sensitivity as detailed below to select one measure for the primary outcome measure. Other measures will be considered for inclusion as secondary outcomes, by considering the ordering of patient scores, and patient willingness to complete different lengths of follow-up surveys. A minimum of one phase 1 outcome measure will be excluded for phase 2.
- 2. Sensitivity of each measure to change by psychosocial interventions. Short-term effectiveness of each intervention will be measured by using the within-person change from baseline to follow-up one, for each phase 1 instrument.

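### As written, phase 2 resource use is scheduled only at the 12-week and 6-month follow-ups and not at the pre-randomisation baseline, so the cost comparison could not be adjusted for prior service use

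*Protocol*

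**What the plan says.** Section 6.6 introduces the phase 2 cost data as "measured using a retrospective resource use questionnaire, an adapted version of the Client Receipt Service Inventory" and attaches no time point to it. The timing comes in the Economic analysis part of the same section: once phase 1 interviews have identified the cost components, "these will then be measured retrospectively at each follow-up point in Phase 2".

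The Follow-ups part defines two such points: "Follow-up 1 - Baseline+ 12 weeks" and "Follow-up 2 - Baseline + 6 months". The Data collection row of the synopsis lists baseline as a separate occasion: "Baseline survey: On entry into the ADAPT trial prior to being randomised to an intervention or the control group".

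On scope, the protocol says "We will estimate costs and outcomes during 'within-trial' period only", and on method "We will undertake a cost consequences analysis, which is used to assess a wide range of costs and consequences (effects) and reports them separately". It states no power, standard deviation or target difference for costs, and describes no adjustment of costs for earlier use.

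**The concern.** One stated reason for the economic analysis is to learn whether the interventions alter later use of health services. Phase 2 is open to people with any systemic autoimmune rheumatic disease, so past admissions, outpatient visits and medication can be expected to vary widely between participants. Where past use predicts later use, a baseline measure is the natural covariate for the cost comparison and the direct check on whether the arms started alike.

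Two features of the plan add to its value. First, allocation is by block randomisation with no stratification stated, so nothing described balances prior use in arms that may be as small as 100. Second, the analysis section makes complete-case analysis the main option and rules out multiple imputation. If heavy users are lost unevenly between arms, randomisation alone does not protect that comparison, and without baseline use the pattern could not be examined directly.

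What is collected cannot be left to a later analysis plan. Once participants have been randomised, prior use could be obtained only by longer recall, after the intervention has begun.

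**Working it through.** **Step 1: is there a baseline measure anywhere?** Setting the places side by side:

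- Economic analysis (section 6.6): resource use is tied to the follow-up points.
- Follow-ups: these are 12 weeks and 6 months after baseline.
- Synopsis, Data collection: the baseline survey is a separate occasion before randomisation, and no resource-use content is listed for it.
- Section 6.6: the phase 1 assessment of costs is qualitative only.
- Section 6.3: phase 1 participants may not enter phase 2.

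So no baseline collection is stated, and phase 1 cannot supply prior use for phase 2 participants.

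**Step 2: inputs for the size of the loss.** The protocol gives no precision figure for costs, so there is none to reproduce. The provisional phase 2 arms in the synopsis are 100 (physical activity), 100 (listening support), 300 (text messages) and 300 (control). They sum to 800, as stated. The correlation r between prior and later cost is not in the protocol. It is an assumption here, taken from 0.1 to 0.7.

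**Step 3: formulas.** In units of the cost SD, for arms of n1 and n0:

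- Unadjusted SE = sqrt(1/n1 + 1/n0)
- SE adjusted for baseline cost = unadjusted SE × sqrt(1 − r²)
- Variance reduction = r²
- Equivalent extra participants without adjustment = 1/(1 − r²) − 1

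These assume linear adjustment with a common variance and slope. With skewed costs they are approximate.

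**Step 4: numbers.** For 100 v 300, sqrt(1/100 + 1/300) = 0.115 SD. At r = 0.5, 0.115 × sqrt(0.75) = 0.100 SD. The 95% half-widths are 1.96 × SE.

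| r | Variance cut | SE, 100 v 300 | Half-width, 100 v 300 | Half-width, 300 v 300 | Equivalent extra participants |
|---|---|---|---|---|---|
| unadjusted | – | 0.115 | 0.226 | 0.160 | – |
| 0.1 | 1% | 0.115 | 0.225 | 0.159 | 1% |
| 0.2 | 4% | 0.113 | 0.222 | 0.157 | 4% |
| 0.3 | 9% | 0.110 | 0.216 | 0.153 | 10% |
| 0.5 | 25% | 0.100 | 0.196 | 0.139 | 33% |
| 0.7 | 49% | 0.082 | 0.162 | 0.114 | 96% |

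The gain therefore runs from next to nothing (r of about 0.2 or less) to large (r near 0.7). The documents do not say where in that range this population lies.

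**The case against.** **Silence is not exclusion.** The sentence on follow-up points may simply describe how within-trial costs are built up. The content of the phase 2 baseline survey is not listed anywhere, and much of phase 2 is deliberately left open until phase 1 reports: cost items, outcomes, sample sizes, even whether there will be separate trials with separate controls. This stands in part. A reader might infer that the protocol rules out a baseline measure, and it does not say so. But the sole timing statement names follow-ups, so a team following the text would not collect it.

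**The comparison is not biased.** This stands. A reader might infer that a chance excess of heavy users in one arm invalidates the cost difference. With full follow-up, randomisation keeps the unadjusted difference unbiased, and its confidence interval already allows for chance imbalance. Nor would imbalance be wholly invisible: baseline EQ-5D-5L, the clinical scales and sociodemographic data can partly show it and partly adjust for it. They are proxies for prior use, not measures of it.

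**The analysis is secondary.** Costs and effects are reported separately, with no cost hypothesis or power stated. The choice of covariates can properly wait for an analysis plan. Both points hold and limit the weight of the concern, but an analysis plan cannot adjust for something never collected.

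**Burden.** The full item list is long, the protocol itself notes debilitating fatigue in lupus patients, and section 6.7 weighs how long a follow-up survey patients will accept. Leaving the section out of baseline could be a reasonable trade-off. That argues for a short baseline section, and for stating the choice.

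**Conclusion.** The point holds as a gap in the data collection schedule. On the text as it stands, prior service use would go unmeasured in phase 2, nothing from phase 1 could replace it, and the cost comparison could not be adjusted for it. The consequence is lost precision, together with a weaker check on imbalance and on selective loss of heavy users. It is not bias in the randomised comparison under full follow-up.

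The size rests wholly on the assumed correlation: a variance reduction of 1% to 49% over r of 0.1 to 0.7, and negligible at about 0.2 or below. The upper figures should not be read as the expected loss, because nothing in the protocol supports a particular r. The 100 v 300 illustration also rests on provisional arm sizes and a shared control, either of which may change. No stated figure is wrong. This is a cheap improvement to a secondary cost consequences analysis, worth making before phase 2 begins.

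**What to change.** In section 6.6, where the resource-use questionnaire is introduced and again under Economic analysis, state that its core health-service items are also completed in the phase 2 baseline survey before randomisation. Use the same wording as at follow-up and a look-back close to the first follow-up interval (12 weeks, so about 3 months). State that baseline cost will be a covariate in the between-arm cost comparison; the form of the model can be left to the analysis plan. If baseline collection was always intended, the same sentence settles the matter.

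The cost is one more section in an online survey that already exists, with no added visit. The real downside is a longer baseline survey for people with fatigue. Limiting the section to the main NHS items (GP and nurse contacts, emergency visits, rheumatology outpatient visits, admissions, medication) and leaving travel, work loss and other out-of-pocket costs to the follow-ups would reduce it.
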